## **Objectives**

### **Overall objectives**

We aim to evaluate whether optimized frequency (compared to the least-optimized frequency) of excitatory TMS will generate better results in behavior and brain activity among healthy participants. Specifically, we will develop a novel tool to compute individualized multi-scale functional connectivity networks using data from baseline resting and task-evoked brain states. Building on that, we will utilize recurrent neural networks (RNN) with long short-term memory (LSTM), a promising deep learning technique, to generate brain decoding models and obtain real-time readouts of brain states. We will then establish a closed loop of rTMS and brain readouts, fine-tuning the rTMS frequency to determine the optimal stimulation frequency for each participant. Participants will receive their optimal stimulation frequency of rTMS over a three-day neuromodulation session and their least optimal stimulation frequency (the frequency least successful in moving their brain state) over another three-day neuromodulation session (order counterbalanced across subjects). We hypothesize that optimal frequency will drive performance improvements and brain changes more than the least optimal frequency.

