### **Primary outcome variable(s)**

Behavior change (task performance) and brain activity change (in-scanner brain readouts during the working memory task or at rest) in response to neuromodulation.

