### **Design**

This study will recruit 38 healthy participants, who will be recruited through the community via study advertisements. Prior to any study visits, all subjects will be pre-screened through a phone interview with a trained member of the study team or an online self-report screening, both through REDCap. The study involves 11 study visits. The first study visit will consist of a consenting and extended screening visit. All participants will have the opportunity to ask questions before signing the electronic consent form. We will complete a semi-structured clinical interview and will demonstrate TMS to ensure the participant is comfortable with all study procedures. This visit will be completed both remote and in- person. The second study visit will involve a 1-hour MRI scan. During the scan, the participant will complete multiple computerized tasks. The MRI scan will include both structural and functional scans, and those scans will be used to localize the stimulation target for the subsequent sessions. The third study visit will be a 2-hour TMS/fMRI session, and the participant will engage in behavioral tasks while interleaved rTMS rounds are delivered at different excitatory frequencies (frequency range: 2Hz-20Hz). This scan will be used to determine the optimal stimulation frequency for the individual participant. The fourth, fifth, and sixth study visits will involve neuromodulation with either the optimized frequency or the frequency least successful in moving a participants brain state, as determined from the third study visit. Each subject will receive ~3000 pulses in each session, including the pulses from the motor threshold determination. We will determine the adjusted MT by using the Stokes equation, which accounts for differences in cortical distance from the site relative to motor cortex (where the motor threshold is found). The stimulation amplitude will be equivalent to 110% of the adjusted MT. Prior studies have safely utilized TMS with such design (VanDerwerker et al., 2018; Cristancho, Trapp, Siddiqi, Dixon, & Lenze, 2018). The seventh study visit will involve a 1-hour TMS/fMRI session while the participant is engaging in a behavioral task.. This visit is designed to examine brain and behavioral changes after the first round of neuromodulation. The seventh and the eighth visit will be scheduled at least one week apart. The eighth, ninth, and tenth study visits will mirror the fourth, fifth, and sixth study visits and will involve neuromodulation with either the optimized or least-optimized individual frequency. The order of optimized and least-optimized frequencies will be counterbalanced across participants between Visit 4-6 and Visit 8-10 (i.e., half of the participants will receive stimulations of the two frequencies in one order, and the other half will receive stimulations of the two frequencies in the reverse order). The

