#### **Resources necessary for human research protection**

Describe research staff and justify that the staff are adequate in number and qualifications to conduct the research. Describe how you will ensure that all staff assisting with the research are adequately informed about the protocol and their research related duties. Please allow adequate time for the researchers to conduct and complete the research. Please confirm that there are adequate facilities for the research.

Staff will be trained on the protocol and inclusion/exclusion criteria. TMS protocols will involve direct training with the Principal Investigator and the study physician, [name]. Facilities will include Penn laboratory spaces specializing in advanced computing and analysis of neuroimaging and cognitive datasets. Scans will be conducted on a Siemens Prisma 3 Tesla whole-body MRI, housed in the Center for Advanced Magnetic Resonance Imaging and Spectroscopy (CAMRIS). Additional MRI resources, such as a mock scanner, may be accessed from the Center for Functional Neuroimaging (CfN).

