## Procedures

All participants will be recruited through the University of Pennsylvania and the surrounding community. Subjects will be pre-screened for eligibility through phone or online self-report screener in REDCap. Eligible subjects will be invited in for a screening visit. Visit 1 will be a consent/ screening session. This visit will involve remote and in-person procedures. During the remote visit, a coordinator will discuss the Informed Consent Form with the participant. After going through the ICF, participants will be asked to electronically sign at the end of the ICF and complete a Remote ICF Attestation form to ensure they understood all the procedures and risk associated with the study. If they agree to participate, they will complete questionnaires related to their medical history, demographics, and eligibility to receive MRI scans and TMS. After completing the questionnaires, participants will undergo a clinical interview. This interview could be done in person or remote. If participants meet eligibility for these initial procedures, we will schedule an in-person meeting to test TMS. For the TMS demo, participants will receive several short rounds of TMS test pulses to the prefrontal cortex to ensure comfort. During this demonstration we will identify the participants resting motor threshold (MT). MT is defined as the minimum magnetic flux needed to elicit a response in a target muscle in 5 out of 10 trials. MT is the standard in the field for measuring cortical excitability and to reduce seizure risk. While TMS is usually quite tolerable, a minority of participants (20%) cannot tolerate stimulation procedures. Screening data will be recorded in REDCap; this data will be retained indefinitely until the study enrollment is completed. The information collected in this initial visit will determine if the subject meets all inclusion criteria. If participants screen-fail or withdraw, we will assign the clinical interview compensation to their virtual Greenphire Clincard. Upon meeting all criteria for inclusion in the study, subjects will then return to complete a 1-hour baseline MRI scan at Visit 2. All MRI imaging protocols will be reviewed and approved by CAMRIS. An experienced technician and a member of the study team will be present during the MR session to ensure participant safety and well-being. If the participant complains of feeling claustrophobic and does not wish to complete the MRI, the study will be terminated. Emergency personnel and equipment are immediately available to the MRI room should the need arise. It is possible that during the course of the research study, the research staff may notice unexpected findings on an MRI scan. Should this occur, the findings will be assessed by a trained radiologist. The study doctor will inform research subjects of any significant findings. Visit 3 will include fMRI and interleaved TMS/fMRI. During this scan, the participant will perform a working memory N-back task several times. Brain data from the baseline MRI scan (stimulation target in individualized brain space) will be calibrated with the skin and scalp using a Polaris Vicra camera (Brainsight neuronavigation) to allow marking of the stimulation site on a swim cap for the TMS/fMRI session. During the MRI scan, participants will receive interleaved TMS/fMRI probes to the brain targets. The purpose of this TMS/fMRI scan is to probe and modulate and measure activity in targeted neural circuits following our established methods (Chen et al., 2013). Moreover, by building brain decoding models using LSTM RNNs deep-learning technique, we can establish a closed loop of rTMS and brain readouts. As a result, we will be able to fine-tune the rTMS frequency to achieve optimal brain state and maximized working memory performance during this session. Our MRI-compatible TMS system (MagPro X100 Stimulator, MRI-B91 TMS coil) is housed in Stellar Chance (SC3T) and the Hospital of the University of Pennsylvania (HUP 6) at the 3-Tesla MRI machine. The apparatus was installed under the supervision of [name]. a member of CAMRIS. TMS in an MRI scanner involves no additional risks to the subject. Visits 4-6 will involve excitatory rTMS delivered in the

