
same interleaved pattern at the same stimulation site as the TMS/fMRI session but with either the optimized frequency determined from that session or the frequency least successful in moving their brain state (half of the participants will receive optimized stimulation frequency, and the other half of the participants will receive least-optimized stimulation frequency during these sessions). The present study utilizes the same FDA-approved devices (Magventure Cool-Coil B65, MagVenture X100 Stimulator) to administer TMS. The TMS system is housed in the Richards Biomedical Building. Only individuals trained by the Principal Investigator ([name].) and, [name] (M.D.) will dispense TMS. In addition to receiving TMS, participants will complete questionnaires and computerized tasks during these visits. The tasks will assess reaction time, working memory, decision-making. The decision-making task will be incentive-based and the amount the participant earns will be added to their final study compensation. During some of the tasks, we may ask subjects to wear a passive eye-tracking device to record the location of your gaze at any particular time. The order of tasks will be randomized for each participant. Visit 7 will involve a 1-hour TMS/fMRI session. Participants will complete the working memory N-back task while inside the scanner. The purpose of this visit is to examine the brain and behavioral changes after the first round of neuromodulation. Visit 8-10 will mirror Visit 4-6 and will involve neuromodulation with either the optimized or least-optimized individual frequency. The order of optimized and least-optimized frequencies will be counterbalanced across participants between Visit 4-6 and Visit 8-10 (i.e., half of the participants will receive stimulations of the two frequencies in one order, and the other half will receive stimulations of the two frequencies in the reverse order). Visit 7 and the Visit 8 will be scheduled at least one week apart. In addition, unless the MRI is unavailable or we encounter scheduling constraints, Visit #3-Visit #7 will be scheduled within the same work week, such as Visit #3 is on Monday, Visits #4-7 are Tuesday/ Wednesday/Thursday, respectively, and Visit #7 is on Friday. Similarly, Visit #8-Visit #10 will be scheduled 4 work-days in a row, either Monday-Thursday or Tuesday-Friday. Visit 11 will mirror Visit 7 and examine brain and behavioral changes after the second round of neuromodulation. Monitoring will include: (1) successful recruitment, retention; (2) subject adherence; (3) safety and tolerability.

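### Visit 3 fixes which frequency is optimal before either round, yet no visible section keeps session staff or analysts unaware of that label, and counterbalancing does not remove an effect tied to it

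*Combined protocol and SAP*

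**What the plan says.** The Design section says of Visit 3: "This scan will be used to determine the optimal stimulation frequency for the individual participant". The same session identifies the frequency least successful in moving the participant's brain state. One of the two is given at Visits 4-6 and the other at Visits 8-10. On how they are allocated, the Design section says only: "The order of optimized and least-optimized frequencies will be counterbalanced across participants between Visit 4-6 and Visit 8-10". The Procedures section repeats this.

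The hypothesis has a direction: "We hypothesize that optimal frequency will drive performance improvements and brain changes more than the least optimal frequency". The primary outcomes are described as "Behavior change (task performance) and brain activity change", the brain part being in-scanner readouts. Working memory is tested at the post-round scan, Visit 7 ("Participants will complete the working memory N-back task while inside the scanner"), and Visit 11 mirrors it. Working-memory tasks are also done at the stimulation visits.

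On staff, the resources section says: "Staff will be trained on the protocol and inclusion/exclusion criteria". The Analysis Plan is one sentence: a time by condition ANOVA on task performance and on voxelwise fMRI responses. It mentions no masked step.

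Random allocation is stated for one thing only: "The order of tasks will be randomized for each participant". The only visible wording about blindness is the exclusion for color blindness. The deception item is answered No.

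**The concern.** The label exists before the first stimulation round, the hypothesis says which label should win, and staff trained on the protocol can know that hypothesis. One primary outcome is task performance, which depends on effort. If the people running a session know that it belongs to the optimal round, encouragement, attention to coil placement or willingness to repeat a task could differ between rounds. If analysts know it, choices about fMRI preprocessing and exclusions are made with the answer in view.

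Either influence would follow the optimal label whichever round came first. A positive result would then have a rival explanation. With no sham or third condition, the planned ANOVA could not separate it from a true frequency effect. The tasks are computerized, so the exposure lies in effort, handling and analytic choices more than in scoring.

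**Working it through.** **Step 1: the text.** The visible document was read for any wording on blinding, masking, concealment or being unaware. There is none beyond the color blindness exclusion. How the order is generated and concealed is also unstated. That is secondary here, because every participant receives both frequencies.

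**Step 2: what counterbalancing removes.** For task performance, the time-by-condition interaction is a paired test on D = (change in the optimal round) minus (change in the least-optimal round), with F(1,27) = t² at n = 28. Let p be an additive period effect (round 2 minus round 1) and b a label-linked shift, both in SD of D. With no true effect:

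- optimal first: mean D = b − p
- optimal second: mean D = b + p
- 14 per order: [14(b − p) + 14(b + p)]/28 = b

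With p = 0.3 and b = 0.2: [14(−0.1) + 14(0.5)]/28 = 0.2. The period effect cancels and the label shift stays. A simulation of 200,000 trials agrees. A period effect of 0.3 alone gives bias 0.00 and rejection 4.1%. A label shift of 0.2 alone gives bias 0.20 and rejection 17.5%. Both together give bias 0.20 and rejection 15.4%.

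**Step 3: two limits on Step 2.**

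- Cancellation needs balance among analysed participants. The protocol enrols 38 to obtain at least 28 usable. With an assumed 17/11 split and p = 0.3, a remainder of 0.3 × (17 − 11)/28 = 0.06 is left.
- The Analysis Plan does not define the pre measurement for round 2. With a shared baseline the label shift enters as b. If Visit 7 served as the round 2 baseline, optimal-first participants would give 2b and the others b. The average is 1.5b, or 0.30 for b = 0.2.

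**Step 4: illustration of size.** From the documents: n = 28. Assumed, because the documents give no alpha, SD or effect size: two-sided 5%, no true effect, and the shifts themselves. The critical value is t(0.975, 27) = 2.052. If a share f of participants carries shift S and the rest none, the mean of D is fS, its variance is 1 + f(1 − f)S², and the noncentrality is √28 × fS / √(1 + f(1 − f)S²).

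| Shift S (SD of D) | All carry it | Half | A quarter |
|---|---|---|---|
| 0.1 | 8.0% | 5.7% | 5.2% |
| 0.2 | 17.5% | 8.0% | 5.7% |
| 0.3 | 33.4% | 11.8% | 6.7% |

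Example: S = 0.2 carried by all gives noncentrality 0.2 × √28 = 1.058 and rejection 17.5%. For S = 0.1, 0.2 and 0.3 carried by all, n = 24 gives 7.6%, 15.6% and 29.1%, and n = 38 gives 9.2%, 22.5% and 43.7%. For scale, the difference detectable with 80% power at n = 28 is about 0.55 SD. The brain-readout outcome is not modelled.

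**The case against.** A reader might infer that the study is open-label, or that participants know which round is meant to work. The documents support neither. No section says that anyone is told the label. What participants are told would be in the consent form, whose pages were removed, so its absence here cannot be held against the plan. The No to deception does not settle it either: withholding the order while saying so in the consent need not be deception.

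It can also be said that both rounds are active stimulation at individually chosen frequencies between 2 and 20 Hz, so knowing the pulse rate does not reveal which rate is optimal. That stands, and it is the reason the label can be masked even though the rate cannot. It does not show that the label is masked.

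The strongest objection is to the size. The shifts are assumed, they are not split between participant and staff routes, and with a quarter of participants affected the error rate stays close to 5%. That stands too: the table shows how sensitive the test is, not how biased this study will be. Nor can it be claimed without qualification that counterbalancing removes every period effect, or that the label shift enters one for one. Both depend on the points in Step 3.

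Finally, this is an exploratory study in healthy volunteers, set out on an application form with no visible field for masking. That explains the silence. It does not change what the ANOVA can distinguish, and the Design, Procedures and Analysis Plan sections are where masking of staff and analysts would be expected.

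**Conclusion.** The point holds as a statement about session staff and analysts: masking to the label is unspecified, and counterbalanced order does not substitute for it. Following the plan as written would leave a rival explanation for a positive result, most clearly on task performance. For participants, the supportable statement is only that their masking needs confirming.

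The size is unknown. Under the stated assumptions the false-positive rate runs from close to nominal (about 6% to 7% if a quarter carry a 0.2 to 0.3 SD shift) to 33% if everyone carries 0.3 SD. No figure in the plan is wrong. The change should be made because it is cheap and because later analysis of the same data cannot separate the two explanations.

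**What to change.** Amend the Design, Procedures and Analysis Plan sections as follows. If any of this is already practised, state it there.

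1. Assign order 1:1 from a computer-generated list in REDCap, revealed only after both Visit 3 frequencies are fixed.
2. Give session operators and task staff only the frequency to deliver, not the label or the Visit 3 readout, as far as existing staffing allows.
3. Do not tell participants which round is optimal, and confirm that the consent says the order is withheld.
4. Code the two conditions separately for each participant. Finalise preprocessing, exclusions and analysis code for Visits 7 and 11 on coded data, and apply the key only after lock. The key is kept under restricted REDCap access by an existing team member who does not process the Visit 7 and 11 behavioural or brain-readout data.
5. Do not ask participants to guess the label before tasks at Visits 4 and 8, since the question would prompt the expectation it is meant to check. If a guess is wanted, ask once after all Visit 11 tasks and report it descriptively, noting that it may reflect a real effect.

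The cost is a short amendment, a coded file, possibly consent wording, and some scheduling effort: Visit 4 normally falls the working day after Visit 3, and staff numbers are not given. Items 3 and 4 do not depend on separating session staff. Masking may stay incomplete. Pulse rate can be perceived, Visit 3 staff see the tuning result, and at Visit 3 participants experience several frequencies while tested ("During this scan, the participant will perform a working memory N-back task several times").

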## **Characteristics of the Study Population**

#### **Target population**

38 healthy control participants to collect useable data from 28 healthy participants.

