#### **Accrual**

All recruitment will be conducted through the University of Pennsylvania and the surrounding community to find a total of 38 healthy participants. It is assumed that there will be some participants who screen fail, are lost to follow up, withdraw, or complete without usable scanner data. Therefore, we estimate that we will need to consent/enroll up to 38 participants overall, in order to adequately test the hypotheses on at least 28 participants.

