**Analysis Plan**

For the primary within-subjects analyses, a time (pre vs post rTMS) by condition (optimized vs least-optimized frequency) ANOVA will be done both on task performance as well as fMRI voxelwise brain responses.

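### Condition order is described only as counterbalanced: no random assignment, concealment or time of assignment is stated, so a possible bias in the crossover contrast is left open

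*Combined protocol and SAP*

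**What the plan says.** Each participant receives both conditions: three days at one frequency (Visits 4-6) and, after a gap of at least one week between Visits 7 and 8, three days at the other (Visits 8-10). Visit 3 supplies the two frequencies; the Procedures section describes the first round as using "either the optimized frequency determined from that session or the frequency least successful in moving their brain state".

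Order is described in three places, in the same terms each time:

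- Overall objectives: "order counterbalanced across subjects".
- Design: "The order of optimized and least-optimized frequencies will be counterbalanced across participants between Visit 4-6 and Visit 8-10", with the gloss that "half of the participants will receive stimulations of the two frequencies in one order" and the other half in the reverse order.
- Procedures: the same statement again, adding that half the participants have the optimized frequency in Visits 4-6.

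No section gives a sequence generator, blocks, concealment, the person who assigns, or the time of assignment. The Procedures section does specify randomisation for something else: "The order of tasks will be randomized for each participant".

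On numbers, the Target population section plans for "38 healthy control participants to collect useable data from 28 healthy participants". The Accrual section counts screen failures, losses to follow-up, withdrawals and unusable scans within the 38. The Analysis Plan is one sentence: "a time (pre vs post rTMS) by condition (optimized vs least-optimized frequency) ANOVA will be done", on task performance and on voxelwise brain response. It has no period or sequence term.

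**The concern.** Equal numbers in the two orders cancel a round effect that is the same for everyone. They do not protect against order groups that differ in how much they change from round 1 to round 2. Random assignment makes that difference zero on average; a half-and-half split by itself does not.

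Such change is plausible here. The N-back is performed several times at Visit 3 and again at Visits 7 and 11, and working memory is also tested during the neuromodulation visits, so practice and scanner habituation may differ between people. By the time order takes effect, the team has seen the participant's Visit 3 performance and brain readouts. If order can be foreseen or chosen then, it may become linked, even unintentionally, to expected change.

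This is the trial's only comparison between conditions, and how order was assigned cannot be repaired after data collection.

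**Working it through.** **Inputs from the documents.** 38 enrolled, 28 usable; two orders, half each; ANOVA with time and condition only. The implied loss is 10/38 = 26.3%. The figure of 28 cannot be reproduced, because no alpha, power, effect size or SD is given. The only stated rate, 20% not tolerating stimulation, would give 28/0.8 = 35, but it covers one cause of loss and so does not contradict 38.

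**Assumptions.** Two-sided alpha 0.05. Let d be a participant's round-2 minus round-1 difference in the outcome analysed, with SD 1 within each order group.

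**Step 1: what the contrast estimates.** With a period term, the condition effect is half the difference between the order groups in mean d. Stable differences between people cancel. If the groups differ in mean d by Δ for reasons unrelated to condition, the bias is Δ/2.

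**Step 2: size at 14 per order.** The standard error is ½ × √(1/14 + 1/14) = 0.189. With no true effect, the rejection rate comes from the noncentral t distribution on 26 df with noncentrality (Δ/2)/0.189:

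| Assumed Δ (SD) | Bias (SD) | Noncentrality | Type I error |
|---|---|---|---|
| 0 | 0 | 0 | 5.0% |
| 0.2 | 0.1 | 0.53 | 8.0% |
| 0.4 | 0.2 | 1.06 | 17.5% |
| 0.6 | 0.3 | 1.59 | 33.3% |

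**Step 3: how strong a link this needs.** Suppose individual between-round change has SD 0.5, in units of the residual SD (assumed), and order has correlation ρ with it. The bias is then about ρ × 0.5 × √(2/π). Simulation at 14/14 with a period term gave:

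| ρ | Bias | Type I error |
|---|---|---|
| 0 | 0.00 | 5.0% |
| 0.3 | 0.12 | 8.5% |
| 0.5 | 0.19 | 14.8% |
| 0.8 | 0.31 | 31.3% |

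Order linked only to a stable trait that does not affect change gave bias 0.00 and 5.1%. Rates in the upper rows therefore need ρ of roughly 0.5 to 0.8, which is strong selection.

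**Step 4: balance after losses.** Assume that order is fixed 19/19 for all 38 at consent and that 10 are lost at random. The number left in one order is hypergeometric (38, 19, 28). P(14/14) = 28.6%. P(16/12 or worse) = 2 × (0.1033 + 0.0273 + 0.0037 + 0.0002) = 26.9%. If order were instead balanced among 34 participants, that probability would be 17.5%; among 30, it would be 0%. These later counts are also assumed.

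**Step 5: what imbalance does.** Let π be the common round-2 minus round-1 shift.

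- Without a period term, as planned: bias = π × (difference in counts)/28. At 16/12 this is 4/28 = 0.14π in absolute size.
- With a period term and random order: no bias. Variance is multiplied by (1/16 + 1/12)/(2/14) = 1.021, about 2% more.

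At 16/12 without a period term the estimate is biased, but simulated type I error stays below 5% (4.0% for π = 0.5, 2.2% for π = 1.0), because the unmodelled shift also enlarges the residual. It exceeds 5% at 19/9 (10.6% and 19.2%), a split with probability of about 2 × 0.0002 = 0.04%.

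**The case against.** Counterbalancing is compatible with balanced random assignment, and the plan is silent on the method. A reader might infer that order is set by hand or is not randomised; the documents support neither. What they support is that randomisation of order is not stated.

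The bias also needs a particular link. Nobody can observe a participant's between-round change at Visit 3, stable differences cancel, and plain alternation gives roughly no correlation unless staff also steer when people enter. This stands, and it is why only the low end of the table is readily plausible.

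A reader might further infer that the bias would favour the optimized frequency, for instance if weak Visit 3 performers or quick learners received it second. That is not established. The Analysis Plan does not define the pre measurement. If it is Visit 3 for round 1, weak scorers would tend to regress upward, and quick learners to gain, in round 1, which would favour the least-optimized frequency.

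On losses, the text speaks of halves of those who receive stimulation, and someone who fails screening needs no order. The 27% figure therefore rests on a timing that the plan does not state, and the resulting bias comes from the missing period term rather than from counterbalancing.

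What remains is that the plan states randomisation for task order and not for condition order, and that a non-random method with equal totals would comply with it.

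**Conclusion.** The concern holds as an unstated safeguard that leaves a possible bias open, in either direction. An order-group difference of 0.2 SD in between-round change would give a bias of 0.1 SD and about 8% type I error, even at 14/14 with a period term. The 17.5% and 33% rates (0.4 and 0.6 SD) are conditional on strong selection and should not be read as expected values. All these differences are assumptions; the documents give no SD and no period effect.

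Imbalance from losses is a secondary matter. If order were fixed for all 38 at consent, a 16/12 or worse split would occur 27% of the time. At 16/12 this adds a bias of 0.14 times the period effect under the planned ANOVA; with a period term and random order it costs only about 2% in variance. The change should be made, because a stated random method is nearly free and cannot be supplied afterwards.

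**What to change.** In Overall objectives, Design and Procedures, replace the counterbalancing statements with: order is randomised 1:1 from a concealed, computer-generated list in permuted blocks of varying size; the next assignment is released only after Visit 3 is complete and the participant's two frequencies have been recorded and locked. Participants lost before that point then use no place on the list.

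In the Analysis Plan, add period and sequence to the time by condition ANOVA, and analyse by the randomised order. The period term is needed in addition to randomisation, because withdrawals and unusable scans after Visit 3 can still unbalance the orders.

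The cost is setting up the list in REDCap, which the study already uses, and a small loss of degrees of freedom (27 to 26 for the condition contrast at n = 28). No visits, participants or staff are added. If the team already intends to randomise order, the change is only to say so and to name the release point.
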